Two study groups will be formed, a control and an intervention group receiving the integrated package of interventions.

The activities of the control and intervention group are summarized in Table 1.

Table 1: Description of Prevention, Screening, Treatment, and Relapse Prevention Activities in the Control and Intervention Groups

	Control*	Mali Intervention
Prevention		
Usual NASG activities (Home visits and group counselling on nutrition and health)	X	X
Integrated NASG (or intensive)		
- NASG created proportionate to population size of village	X	
- Frequent home visits (once a month)	X	
- Strengthening of group counselling / cooking demonstrations activities	X	
- Distribution of SQ-LNS to 6-17-month children	X	
Screening		
Usual activities of the NASGs (screening using MUAC criterion during home visits and group counselling)	X	X
Family MUAC		X
Screening with Weight-for-height / MUAC during the 7th month of the IRAM project	X	X
Treatment		
National CMAM Program (CSCOM and CHW Site)	X	X
Integrated NASG (or intensive)		

Follow-up of cases under treatment by intensive home visits (twice a month)	X
Relapse prevention	
Integrated NASG (or intensive)	
-Intensive home visits (twice a month)	X
-Distribution of nutritional supplements to 6–24-month children post-treatment	X

*In Koutiala villages, NASGs were created by the health district and UNICEF in 2019. However, their monitoring was stopped in 2019. It is not known at this time whether the NASGs are still operational.

The study was designed as a two-arm, cluster-randomized, nonblinded effectiveness study. A cluster-randomized design was used because individual randomization of the NASG intervention was not feasible. A cluster was defined as the catchment area of a first-line health center. All health center catchment areas included in the study were first grouped into 4 strata according to their characteristics to obtain a more balanced randomization result.

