A population-representative longitudinal study design (**Cohort 1 or Main cohort**) was used enrolling children aged 6 to 6.9 months from May 2021 until November 2021. In addition, a second cohort (**cohort 2 or Treatment cohort**) was constituted consisting of all children admitted to MAM OTP (French: URENAM) and SAM OTP (French: URENAS) provided by first-line health centers and community health workers from May 2021 until February 2022. Finally, study field workers home visited a subsample of children three months after their discharge from SAM or MAM OTP to assess the impact of the intervention on post-treatment relapse rates (**cohort 3 or Relapse prevention study**). While the Main cohort study is an experimental study³, the Treatment cohort and Relapse prevention study are quasi-experimental in nature. The quasi-experimental character of these two sub-studies implies that the random character of the intervention and comparison group is not fully guaranteed. More precisely, children enrolled in the Treatment cohort may not be comparable between study groups because the BCC and SQ-LNS may prevent a proportion of the usual prevalence of wasting. Similarly, a higher screening coverage or screening by family MUAC may refer children with wasting with different characteristics as compared to those in the comparison group. Therefore, any impact or lack of impact of the NASG intervention to support the OTP services needs to be interpreted with caution, as it may be a result of both the intervention and any different characteristics of the enrolled samples of children. For the same reasons, the results of the relapse prevention study must be interpreted bearing in mind possible impacts of the preceding preventive BCC and SQ-LNS and improved screening and referral (studied in the main cohort), as well as possible impacts on the adherence and recovery rates of MAM and SAM OTP (studied in the treatment cohort).

Study outcomes

Primary study outcomes

1. The longitudinal prevalence of wasting in children enrolled at the age of 6 months followed monthly until the age of 12 months or until the end of the study, whatever comes first (**cohort 1 or Main cohort**). This indicator is defined for each child as the number of visits during which nutritional wasting is observed divided by the total number of monthly visits made (by the interviewers).

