2. The recovery rate in children enrolled at the age of 6-23 months for a treatment of up to 3 months in URENAM and URENAS treatment services and followed until their discharge (**cohort 2 or**

³ The main cohort study is an experimental cluster-randomized controlled study that guarantees (if random allocation of clusters is successful) that the samples of children enrolled in the intervention and comparison group have similar household, caregiver, and child characteristics. Therefore, any observed impacts can be exclusively associated with the intervention.

Treatment cohort). This indicator is defined as the number of children declared recovered from wasting according to the criteria of the national program (WLZ-score \geq -1.5 or MUAC \geq 125mm, and absence of bilateral edema during two consecutive visits, within 12 weeks after enrollment in the program) divided by the total number of enrolled children.

3. The prevalence of relapse after URENAS or URENAM treatment defined as the proportion of children (9-18 months of age) with WLZ-score <-2 or MUAC <125 mm or bilateral pitting edema three months after discharge from SAM or MAM OTP (**cohort 3 or Relapse Prevention study**).

Secondary study outcomes

For Cohort 1

- The longitudinal prevalence of:
 - o MAM defined as the number of MAM diagnoses divided by the total number of monthly visits made by the survey teams.
 - o SAM defined by the number of SAM diagnoses divided by the total number of monthly visits made.
- The incidence of:
 - o Wasting defined as the number of new cases of wasting diagnosed during the monthly visits made by the survey teams.
 - o MAM defined as the number of new MAM cases diagnosed during the monthly visits made by the survey teams.
 - o SAM defined as the number of new SAM cases diagnosed during the monthly visits made by the survey teams.
- The prevalence of anemia and severe anemia defined as the proportion of children with a hemoglobin level below 11g/dL and 7 g/dL respectively, at age of 12 months or at the end of the study.
- The mean hemoglobin concentration at age of 12 months or until or at the end of the study.
- The prevalence of stunting defined as the proportion of children with LAZ <-2 (according to the 2006 WHO reference) at age of 12 months or at the end of the study.

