where C_{in} = current wasting, SAM or MAM cases in SAM or MAM OTP, C_{out} = current wasting, SAM or MAM cases not in SAM or MAM OTP, R_{in} = recovering wasting, SAM or MAM cases in SAM or MAM OTP, and R_{out} = recovering wasting, SAM or MAM cases not SAM or MAM OTP estimated for World Vision screening campaigns as $\frac{1}{k} \times (R_{in} \times \frac{C_{in} + C_{out}}{C_{in}} - R_{in})$ and k = the mean length of a recovered episode of wasting, assumed to be 5.1 months for MAM and 5.7 months for SAM based on a previous longitudinal study conducted in an adjacent region¹⁰. For single coverage estimate using the Main cohort data, R_{out} is estimated by observing recovery between two monthly measurements.

Data management

The management of all research data will follow IFPRI's institutional research data management protocol, overseen by the IFPRI Data Governance Committee, as well as UNICEF data governance standards. All received data will be carefully anonymized and de-identified so that the privacy of participants and research subjects is fully protected. Personally Identifiable Information data (PII; names, telephone numbers, GPS coordinates, date of birth) will be stripped from the research data when receiving the data on the server. During data collection, PII data will be stored in a separate secured server folder accessible only to the Principal Investigators. PII data will only be used to identify a household to conduct additional verification of previously collected data. When data collection and data validation have been completed, PII data will be destroyed.

In accordance with IFPRI's policy on research data management and open access, at the time of publication of scientific articles presenting the primary results, fully anonymized databases will become a public good and will therefore be made available to the scientific community, government, partners.

All data collection is scheduled to start once the study trial is registered on clinicaltrials.gov.

Statistical analysis

Data sources

The training of NASG groups is scheduled to be concluded in the last week of July 2021. Therefore, cohort 1 and 2 data from May to July 2021 will be used to assess the study baseline and to inspect imbalances in sample characteristics between study arms. Follow-up data from August 2021 to February 2022 will be

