⁹ Balegamire S, Siling K, Alvarez JL, Guevarra E, Woodhead S, Norris A. 2015. "A Single Coverage Estimator for Use in SQUEAC, SLEAC, and Other CMAM Coverage Assessments." *Field Exchange*, vol. 49

¹⁰ Barba, Francisco M., Lieven Huybrechts, and Jef L. Leroy. 2020. "Incidence Correction Factors for Moderate and Severe Acute Child Malnutrition From 2 Longitudinal Cohorts in Mali and Burkina Faso." *American Journal of Epidemiology* 189(12): 1623–27

used to assess the impact of the program. For cohort 3, data from October 2021 to February 2022 will be used to study the impact of the intervention on relapse.

Guiding principles and analysis strategy

Data will be analyzed on intent-to-treat basis. To allow for an analysis “as randomized” in the presence of missing data, we will impute missing data of the primary outcomes of the longitudinal study using a multiple imputation strategy under the *missing at random* assumption. Data management, data cleaning, and statistical analyses will be done using Stata 17.0 (Statacorp, USA). The statistical significance will be set at 5%. All statistical tests will be two-sided. The analysis of primary study outcomes will not be adjusted for multiple testing (n=3 primary study outcomes) given the data involved represent three distinct experimental and control study arms with each one primary study outcome.

We present results from non-adjusted and adjusted linear mixed effects regression models. The non-adjusted models use *health center catchment area* as a random intercept and sampling stratum as a fixed effect to represent the study design. Adjusted regression models further include as fixed effects the cluster baseline means (May-July 2021 period) of the outcome under analysis, month of enrollment into the study (cohort effect), child sex, child age, and primiparity. Furthermore, if any baseline household, caregiver or child characteristic is imbalanced (absolute difference of ~5pp) between study groups, we conduct an additional robustness analysis adjusting the analysis for this covariate.

Cohort 1 specific considerations

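### The adjusted model for primary outcome 2 uses a May-July mean of recovery with no stated indexing date; indexed by admission, that mean is partly post-treatment and shrinks the adjusted effect

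*SAP*

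**What the plan says.** Under Guiding principles and analysis strategy, the SAP announces two sets of results: "We present results from non-adjusted and adjusted linear mixed effects regression models". Neither is named as primary. The adjusted model adds several fixed effects, the first being "the cluster baseline means (May-July 2021 period) of the outcome under analysis". No exception is made for cohort 2.

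Under Primary study outcomes, recovery requires the anthropometric criterion and "absence of bilateral edema during two consecutive visits, within 12 weeks after enrollment in the program". The count of recovered children is "divided by the total number of enrolled children". Under Study design, cohort 2 consists of children admitted to treatment "from May 2021 until February 2022".

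Under Data sources, "cohort 1 and 2 data from May to July 2021 will be used to assess the study baseline", and data from August 2021 to February 2022 are used for impact. Cohort 1 specific considerations gives 1 August 2021 as the start of the programme. Table 1 lists twice-monthly home visits to cases already under treatment for one group only, and Study objectives makes follow-up visits to wasting cases part of the package.

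**The concern.** A baseline covariate is safe to adjust for because the intervention cannot have touched it. Most items in the SAP's baseline table are known at enrollment. Recovery is not: it is decided up to 12 weeks later. A child admitted in June or July can still be in treatment when the home visits begin in the intervention areas.

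If the May-July mean includes such children with their eventual outcome, it holds part of the intervention effect in one arm and none in the other. Conditioning on it then removes some of the effect being estimated. A reader comparing the two models might put the gap down to chance baseline imbalance. The outcome is one of three primary outcomes, and the SAP does not say which model leads.

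**Working it through.** **The plan's own figure.** For cohort 2, version 2.0 gives 42 clusters of 50 cases over 7 months, 79% cure, ICC 0.05, 80% power and two-sided 5%, with a detectable difference of about 9.0 points. The design effect is 1 + 49 × 0.05 = 3.45, so the effective size per arm is 21 × 50 / 3.45 = 304. Solving for the difference gives 8.4-8.6 points for an increase and 9.9-10.2 for a decrease. The stated 9.0 is not matched exactly, but it is on the cautious side for an increase. It serves below only as a reference effect.

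**Open windows on 1 August (admission indexing).** May to July has 92 days. An 84-day window opened on 9 May reaches 1 August, so only admissions of 1-8 May close earlier. The open share is 84/92 = 91%. This is an upper bound, because 12 weeks is the longest time allowed.

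**Children actually in treatment on 1 August.** The SAP gives no length of stay. With even admissions and a stay of D days, the share is D/92:
- 28 days: 30%
- 42 days: 46%
- 56 days: 61%

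It passes one half only when stays exceed 46 days.

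**Share of the effect in the baseline mean.** If the effect accrues in proportion to treatment time after 1 August, the average share is f = D/(2 × 92): 0.228 for 42 days, 0.304 for 56 and 0.457 for 84.

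**Slope on the baseline mean.** Baseline cases per cluster: 50 × 3/7 = 21.4. With stable area effects the slope equals the reliability, r = 21.4 × 0.05 / (1 + 20.4 × 0.05) = 0.53.

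**Expected adjusted effect,** 9 × (1 − r × f):
- 42 days: 9 × (1 − 0.53 × 0.228) = 7.9 points
- 56 days: 9 × (1 − 0.53 × 0.304) = 7.5 to 7.6 points
- 84 days: 9 × (1 − 0.53 × 0.457) = 6.8 points

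**Simulation.** 42 clusters, 21 baseline and 50 follow-up cases each, least squares on cluster means, 4,000 runs per scenario. With f = 0 the adjusted estimate was 8.9, the same as the unadjusted one. With f = 0.228 it was 7.9, and with f = 0.457 it was 6.8, against unadjusted estimates of about 8.8.

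**Sensitivity (42-day and 84-day stays).**
- ICC 0.02 (r = 0.30): 8.4 and 7.8. ICC 0.10 (r = 0.70): 7.5 and 6.1.
- The SAP's district caseload instead (1,750 cases over 8 months, so 1,750/8 × 3/42 = 15.6 per cluster; r = 0.45): 8.1 and 7.2.
- Area effects correlated only 0.5 between periods (assumption; slope 0.265): 9 × (1 − 0.265 × 0.228) = 8.5 and 9 × (1 − 0.265 × 0.457) = 7.9.
- Every child still in treatment on 1 August gets the full effect (f = D/92): 6.8 and 4.6. Nothing in the SAP supports so strong an assumption.

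**Outcome-date indexing.** If only outcomes recorded by 31 July enter the mean, f = 0 and there is no attenuation.

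**The case against.** The strongest reply is that the SAP never says the mean is built by admission date. Data sources divides cohort 2 data by calendar period. Baseline characteristics describes values collected before the intervention began. Registers are copied weekly at health centers and monthly at community sites, so outcomes on file by 31 July form a natural data set. On that reading the problem disappears. This stands, and it makes the concern conditional.

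It does not settle the matter. Cohort 2 is defined by admission, the denominator is enrolled children, and the adjusted model also uses month of enrollment. The Baseline characteristics section speaks of values at enrollment, and recovery has none. Outcome-date indexing leaves its own gap: June-July admissions still in treatment are either dropped or counted as not recovered, and the SAP does not say which.

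The covariate list is also plainly generic. Primiparity is tabulated only for cohorts 1 and 3, and cohort 3 has no May-July outcome. That makes it less likely that the rule was thought through for recovery, but it does not supply the missing definition.

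On size, a 9-point detectable difference implies a standard error near 9/2.8 = 3.2 points. The losses of 1.1 and 2.2 points are therefore about 0.3 and 0.7 of a standard error. The non-adjusted result is always shown alongside, and the SAP itself calls cohort 2 quasi-experimental and asks for caution. These points limit the consequences. They do not justify keeping a covariate that may be post-treatment.

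**Conclusion.** The concern holds in conditional form. The baseline mean of recovery is undefined, and one natural reading makes it partly post-treatment in the intervention arm, with the adjusted estimate pulled toward zero. Under that reading a true 9-point effect becomes about 7.9 points (42-day stays) to 6.8 points (84-day stays), and is less attenuated if area effects change over time. These figures assume even admissions, the stay lengths used, ICC 0.05, about 21 baseline cases per cluster, stable area effects and proportional accrual.

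Two stronger inferences are not supported. A reader might conclude that the adjusted analysis is biased as planned; that requires admission indexing, which the SAP does not fix. A reader might also conclude that most of the baseline is decided after the start. The 91% counts open windows, not late outcomes, and a majority needs stays longer than about 46 days, a figure the SAP does not give. The non-adjusted analysis of outcome 2 is not affected. The point merits a correction to the SAP because it bears on a presented analysis of a primary outcome.

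**What to change.** Add one sentence to Guiding principles and analysis strategy: for cohort 2, the cluster baseline mean of recovery is computed only from episodes whose outcome (recovery, default, death or transfer) was decided by 31 July 2021, and episodes open after that date do not contribute. If this leaves too few episodes per cluster, omit the covariate for outcome 2.

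The cost is a noisier covariate that over-represents short stays, in both arms alike. It should be described as a pre-programme prognostic covariate, not as the recovery rate defined for the primary outcome. Some of the precision gain from adjustment is lost, or all of the gain from this covariate if it is dropped. The non-adjusted model needs no change.

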Considering a baseline longitudinal prevalence of 13.2% (obtained from the control group of the PROMIS Mali study) with a standard deviation (SD) of 0.239 for the control group and an SD of 0.189 for the treatment group, a mean cluster size of 55 (anticipating a loss of follow-up of 15%), a statistical power of 80%, a type I error of 5% and an intra-cluster coefficient of 0.04, we need at least 42 clusters to detect a minimum difference of ~ 4.55 percentage points, , which is equivalent to a relative risk of 0.65.

Cohort 2 - Primary Outcome: recovery Rate

The aim is to include all URENAS and URENAM treatment data for children between 6 and 23 months of age. Using 2019 health district statistics, the total number of SAM and MAM cases (6-23 months of age) over 8 months of follow-up was estimated at 750 and 1,000 respectively.

Scenario with 45 clusters available (SAP version 1.0)

With 44 clusters that each have an average of 35 cases of SAM and MAM over a 7-month period, assuming a URENAS/URENAM cure rate of 79%, a statistical power of 80%, a type I error of 5% and an intra-cluster coefficient of 0.05, a minimum difference of ~9.0 percentage points in the URENAS/URENAM cure rate could be detected in children aged 6-23 months.

Scenario with 42 clusters available (SAP version 2.0)

With 42 clusters that each have an average of 50 cases of SAM and MAM over a 7-month period, assuming a URENAS/URENAM cure rate of 79%, a statistical power of 80%, a type I error of 5% and an intra-cluster coefficient of 0.05, a minimum difference of ~9.0 percentage points in the URENAS/URENAM cure rate could be detected in children aged 6-23 months.

Cohort 3 - Primary Outcome: Prevalence of Relapse

Scenario with 45 clusters available (SAP version 1.0)

We considered a 35% prevalence of relapse in children aged 9-17 months, three months after treatment completion (estimate obtained in the control group of the PROMIS Mali study). We need a minimum of 44 clusters with a mean cluster size of 20 (anticipating a 15% loss of follow-up), a statistical power of 80%, a type I error of 5% and an intra-cluster coefficient of 0.04 to detect a minimum difference of ~ 12.0 percentage points in the 9-18⁵ months age group.

Scenario with 42 clusters available (SAP version 2.0)

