Children are enrolled in the study cohort at the age of 6 months, when the program foresees MUAC screening measurements and SQ-LNS distribution by NASG to start. From August 1th, 2021 (start of the program) onwards, NASG in both intervention and comparison study arms are tasked to conduct home visits to pregnant and lactating women and caregivers of children up to 24 months of age to provide BCC on child nutrition, health and WASH. Therefore, it is likely that caregivers with children of 6 months enrolled in the cohort after the start of the program have been exposed to BCC prior to study inclusion. This exposure to BCC may have been greater in the intervention group because in that study group the program formed new NASGs proportionate to village population size (contrary to the comparison group with typically counts 1-2 NASG per village independent of population size). For this reason, all analyses related to study outcomes on the impact pathway related to BCC (knowledge indicators, IYCF, immunization rates, WASH practices, child anthropometry) include the data at enrollment at the age of 6 months. For study outcomes related to activities that only start between the age of 6 and 7 months, like MUAC-based screening and the distribution of SQ-LNS, we consider data related to the program’s impact from the child age of 7 months onwards. To assess the intervention’s impact between study enrollment (child age of 6 months) until the end of the study (9 to 12 months of age)

Treatment of missing data for primary study outcomes

We conducted multiple imputation of missing longitudinal anthropometric data using fully conditional specification, also known as multiple imputation by chained equations which imputes missing values

under the missing at random assumption¹¹. Imputation variables were the wide-form anthropometric measurements and child age, and complete predictors (independent variables) were child sex and randomization stratum. We used 50 imputations with 10 burn-in iterations to allow for convergence to a stationary distribution before the imputation. Imputation quality will be assessed using trace plots by iteration to assess convergence and using box plots to compare distributions of observed and imputed values.

Statistical analysis methods

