For the analysis of the longitudinal prevalence of wasting (primary outcome), severe and moderate acute malnutrition and morbidity, the incidence of acute malnutrition and wasting we use mixed-effects Poisson regression models with robust estimation of standard errors to provide adjusted risk estimates. Results from non-adjusted and adjusted regression models will be presented as described under the paragraph on 'Guiding principles and analysis strategy'.

Continuous outcomes (such as WLZ, MUAC, LAZ) that are measured monthly will be regressed over calendar date using a linear mixed-effects model including *health center catchment area* and *child* as a random intercept and *follow-up time* as a random slope. For each model, we assess if the addition of a quadratic term of time improves the model fit significantly by applying a likelihood ratio test comparing the model with and without the quadratic term. To assess the specific impact of the intervention (SQ-LNS, MUAC screening and BCC) from enrollment at the age of 6 months to the end of follow-up, we assess the interaction between intervention allocation and time.

Dichotomous outcomes will be analyzed using linear probability mixed-effects models with robust estimation of the standard errors with *health center catchment area* as random effect and sampling stratum as fixed effect to demonstrate the impact of the intervention on the dichotomous outcome averaged over the follow-up period or at the end of the study. For repeated measures, to assess the specific impact of the intervention (SQ-LNS, MUAC screening and BCC) from enrollment at the age of 6 months to the end of follow-up (cohort 1), we assess the interaction between intervention allocation and follow-up time using a linear probability mixed-effects model with *health center catchment area* and *child* as a random intercepts and *follow-up time* as random slope.

Considerations for analysis

Baseline characteristics

For all variables measured, the available values at enrollment and collected from May to July 2021, i.e. before the start of the intervention, will be considered as baseline characteristics. The background characteristics of subjects who completed the study will be presented by intervention group. Following CONSORT guidelines, no statistical tests will be conducted comparing baseline characteristics between

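### The imputation model for the cohort 1 primary outcome leaves out study arm, so a real effect is diluted toward no difference

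*SAP*

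**What the plan says.** Under Guiding principles and analysis strategy, the SAP gives the aim as an as-randomized analysis despite missing data: "we will impute missing data of the primary outcomes of the longitudinal study using a multiple imputation strategy", under missing at random. Under Cohort 1 specific considerations, Treatment of missing data for primary study outcomes, it specifies chained equations with 50 imputations and 10 burn-in iterations, and then the contents of the model: "Imputation variables were the wide-form anthropometric measurements and child age, and complete predictors (independent variables) were child sex and randomization stratum". It mentions neither study arm, nor imputation by arm, nor health center catchment area.

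The analysis that follows needs both. For the primary outcome, "we use mixed-effects Poisson regression models with robust estimation of standard errors to provide adjusted risk estimates" (Statistical analysis methods), and the models take catchment area "as a random intercept and sampling stratum as a fixed effect to represent the study design" (Guiding principles). The Randomization section says that allocation was done separately in each stratum, so knowing a child's stratum says nothing about the child's arm.

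**The concern.** An imputation model without arm assumes that, given a child's other measurements, age, sex and stratum, the missing values have the same distribution in both arms. If the intervention works, that holds only as far as the child's observed visits already show the effect. The SAP itself gives reason to doubt this: it describes "activities that only start between the age of 6 and 7 months, like MUAC-based screening and the distribution of SQ-LNS". A child lost soon after enrolment has few visits that carry an arm difference, and the later ones are drawn from a mixture of intervention and control children. The imputed part of the data then shows too small a difference.

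What is at stake is the primary outcome of the only cohort that the SAP calls experimental, in a design with about 80% power and little to spare. The imputation is there to restore the as-randomized comparison, and as specified it may not do so.

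**Working it through.** **Inputs from the SAP (Sample Size, cohort 1).** Control longitudinal prevalence 13.2%; SD 0.239 (control) and 0.189 (intervention); ICC 0.04; 15% loss to follow-up; two-sided 5%; 42 clusters of 55; detectable difference 4.55 points. Monthly visits from 6 to 12 months give at most 7 visits. The split of the 42 clusters is not stated; 21 per arm is assumed.

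**Reproducing the plan's figure.** SE = sqrt[(0.239² + 0.189²) × (1 + (m − 1) × 0.04) / (clusters per arm × m)].

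- Version 1.0, 44 × 35: with t quantiles on 42 df the detectable difference is 4.84 points, as stated.
- Version 2.0, 42 × 55: SE = sqrt(0.092842 × 3.16 / 1155) = 0.0159. The detectable difference is 4.58 points (t, 40 df) or 4.47 (normal), against about 4.55 stated.
- Power at 4.55 points: 79.6% (t) or about 81% (normal). Relative risk: (13.2 − 4.55)/13.2 = 0.655.

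**Amount missing.** If 15% of children drop out at a time spread evenly over visits 2 to 7, each loses 3.5 of 7 visits on average, so 0.15 × 0.5 = 7.5% of due visits are missing.

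**Simulation at the trial's size.** 42 clusters of 55, 7 visits, a latent score of weight-for-length type. Within-child correlation was set to give the control SD of 0.239 and ICC of 0.04, and the effect was set to 4.55 points. Two correlation structures were used, with 120 replicates and Monte Carlo error of about 0.4%. Dropout was random. The table gives each estimate as a share of the full-data effect.

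| Effect shape | SAP model (no arm) | Arm added | Available visits only |
|---|---|---|---|
| Constant from first visit | 0.974-0.981 | 0.993 | 0.992-0.997 |
| Starts at 7 months | 0.944-0.950 | 0.993-0.994 | 0.946-0.952 |
| Builds up over follow-up | 0.908-0.919 | 0.990-0.994 | 0.911-0.915 |

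Multiplying 4.55 by the SAP-model column gives about 4.4-4.5, 4.3 and 4.1-4.2 points. With SE held at 1.59 points, power by the normal formula is 79-80%, 77% and 74-75%.

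**Variations.**

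- Staggered entry, with only due visits counted (4 to 7 per child): 0.978, 0.949 and 0.919 without arm.
- All losses after visit 1 or 2 (0.15 × 5.5/7 = 12% of visits missing): 0.956, 0.900 and 0.868 without arm, against 0.98-0.99 with arm.
- No true effect: the mean arm difference was 0.0024 with and without missing data, so the imputation adds no arm bias.
- Catchment area omitted: SE 0.3-1.1% below full data at even dropout timing, about 3% if all losses are early.
- Cluster indicators in the imputation (60 replicates): 0.98-0.99 of the effect kept, SE 0.4-0.9% above full data.

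**Second simulation by a different method.** 600,000 children without clustering, each missing visit regressed on the child's earlier visits. With 15% lost evenly over visits, leaving arm out shrank the effect by 1-5% if it was present at enrolment and by 5-8% if it built up. With 15% seen only at enrolment, the shrinkage was 3-10% and about 15%; with late losses it was 0.4-3%. Adding arm brought the shift to about zero in every case (−1.9% to +1.3%, simulation noise).

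**The case against.** The omission itself is hard to dispute; the case on the other side concerns its size.

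- **The milder case may apply.** The same SAP section says that caregivers enrolled after program start may already have received counselling, possibly more of it in the intervention arm, and for that reason it includes enrolment data in analyses of child anthropometry. An arm difference could therefore exist at the first visit. This stands: if the effect is constant from then on, only about 1-3% is lost and the fix gains almost nothing. It does not exclude a later effect of the supplement, and the SAP plans an arm-by-time interaction.
- **Dropout, not imputation, causes most of the loss.** For effects that start later, the SAP's model and the available-visits ratio give nearly the same estimate. This is correct, and it means that the imputation fails to recover the loss. But recovering it is what the SAP says imputation is for, and with a constant effect the arm-free model does slightly worse than no imputation (97-98% against 99-100%).
- **Catchment area is a variance matter.** Agreed. It does not pull the effect toward zero, and it is minor.
- **The starting power depends on the formula.** By the t version it is 79.6%, not 81%; under even dropout, power without arm is then 73-79%. The conclusion does not change.
- **The direction is conservative.** True, but a diluted primary estimate and lost power are still avoidable faults.

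**Conclusion.** The concern holds. The SAP gives what reads as a complete imputation model, study arm is not in it, and nothing elsewhere supplies it. Under a real effect, the cohort 1 estimate is biased toward no difference. At the planned 15% loss with evenly spread dropout, about 2-3% of the effect is lost if it is constant, 5-6% if it starts at 7 months and 8-9% if it builds up. Power falls by between 1 and about 7 points. The loss is larger if children leave soon after enrolment and smaller if they leave late.

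These sizes rest on assumed effect shapes, visit correlations and dropout timing, and on dropout unrelated to arm or nutritional status. Only the prevalence, SDs, ICC, cluster numbers, loss rate and target difference come from the SAP. The point should be fixed, but it does not threaten the type I error of the trial.

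**What to change.** - Include study arm in every imputation equation, or impute separately by arm.
- Represent catchment area as a random effect, or as cluster indicators within arm. Indicators over all clusters already contain arm and stratum, so they replace those terms.
- State that only visits due "until the age of 12 months or until the end of the study, whatever comes first" enter the imputed outcome, so that late-enrolled children are not given visits they were never meant to have.
- The SAP mixes tenses on whether imputation has been carried out. If it has, report the result under the model now in the SAP and the available-visits result beside the revised one, so that the change is open to inspection.

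The cost is revised SAP wording and a re-run of the imputation code; no new data are needed. With cluster indicators, the SE was about 1-2% larger than under the SAP's model.
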